## 16.2.8 Table A8 Management of Hematologic irAEs in Patients Treated With ICPis

8.0 Hematologic Toxicities	
8.1 Autoimmune hemolytic anemia	
Definition: A condition in which RBCs are destroyed and removed from the blood stream before their normal lifespan is over. Symptoms include weakness, paleness, jaundice, dark-colored urine, fever, inability to do physical activity, and heart murmur.	

Diagnostic work-up
 
History and physical examination (with special consideration of history of new drugs and insect, spider, or snake bites)
 
Blood chemistry, CBC with evidence of anemia, macrocytosis, evidence of hemolysis on peripheral smear; LDH, haptoglobin, bilirubin, reticulocyte count, free Hgb DIC panel, which could include PTNIR infectious causes
 
Autoimmune serology
 
Paroxysmal nocturnal hemoglobinuria screening
 
Direct and indirect bilirubin; LDH; direct agglutinin test; and if no obvious cause, bone marrow analysis, cytogenetic analysis to evaluate for myelodysplastic syndromes
 
Evaluation for viral/bacterial (mycoplasma, etc) causes of hemolysis studies
 
Protein electrophoresis, cryoglobulin analysis
 
Work-up for bone marrow failure syndrome if refractory, including B12, folate, copper, parvovirus, FE, thyroid, infection
 
Glucose-6-phosphate dehydrogenase
 
Evaluation of common drug causes (ribavirin, rifampin, dapsone, interferon, cephalosporins, penicillins, NSAIDs, quinine/quinidine, fludarabine, ciprofloxacin, lorazepam, diclofenac, etc)
 
Assessment of methemoglobinemia
	
Grading	Management
G1: Hgb < LLN to 10.0 g/dL; < LLN to 6.2 mmol/L; < LLN to 100 g/L	Continue ICPi with close clinical follow-up and laboratory evaluation
G2: Hgb < 10.0 to 8.0 g/dL; < 6.2 to 4.9 mmol/L; < 100 to 80 g/L	Hold ICPi and strongly consider permanent discontinuation Administer 0.5-1 mg/kg/d prednisone equivalents
G3: Hgb < 8.0 g/dL; < 4.9 mmol/L; < 80 g/L; transfusion indicated	Permanently discontinue ICPi Should use clinical judgment and consider admitting the patient Hematology consult Prednisone 1-2 mg/kg/d (oral or IV depending on symptoms/speed of development) If worsening or no improvement, 1-2 mg/kg/d prednisone equivalents and permanently discontinue ICPi treatment Consider RBC transfusion per existing guidelines; do not transfuse more than the minimum number of RBC units necessary to relieve symptoms of anemia or to return a patient to a safe Hgb range (7-8 g/dL in stable, noncardiac inpatients) Should offer patients supplementation with folic acid 1 mg once daily
G4: Life-threatening consequences, urgent intervention indicated	Permanently discontinue ICPi Admit patient Hematology consult IV prednisone corticosteroids 1-2 mg/kg/d If no improvement or if worsening while on corticosteroids or severe symptoms on presentation, initiate other immunosuppressive drugs, such as

8.0 Hematologic Toxicities	
	rituximab, IVIG, cyclosporin A, and mycophenolate mofetil RBC transfusion per existing guidelines; discuss with blood bank team prior to transfusions that a patient with possible ICPI serious AE is in house.
Additional considerations: Monitor Hgb levels on a weekly basis until the corticosteroid tapering process is complete; thereafter, less-frequent testing is needed	
8.2 Acquired TTP	
Definition: A disorder characterized by the presence of microangiopathic hemolytic anemia, thrombocytopenic purpura, fever, renal abnormalities, and neurologic abnormalities, such as seizures, hemiplegia, and visual disturbances. It is an acute or subacute condition.	
Diagnostic work-up History with specific questions related to drug exposure (eg, chemotherapy, sirolimus, tacrolimus, opana ER antibiotics, quinine) Physical examination, peripheral smear ADAMTS13 activity level and inhibitor titer LDH, haptoglobin, reticulocyte count, bilirubin, urinalysis to rule out other causes PT, activated PTT, fibrinogen Blood group and antibody screen, direct antiglobulin test, CMV serology Consider CT/MRI brain, echocardiogram, ECG Viral studies Note: This disorder is usually associated with a severe drop in platelets and hemolysis/anemia precipitously	
Grading	Management
All grades	The first step in the management of TTP is a high index of suspicion for the diagnosis and timely recognition; hematology consult should immediately be called, as delay in identification is associated with increased mortality/morbidity. Initially, the patient should be stabilized and any critical organ dysfunction stabilized
G1: Evidence of RBC destruction (schistocytosis) without anemia, renal insufficiency, or thrombocytopenia clinically G2: Evidence of RBC destruction (schistocytosis) without clinical consequence with G2 anemia and thrombocytopenia	Hold ICPI and discuss resumption with patient only after taking into account the risks and benefits, noting that there are currently no data to recommend restarting ICPI therapy Hematology consult Administer 0.5-1 mg/kg/d prednisone
G3: Laboratory findings with clinical consequences (G3 thrombocytopenia, anemia, renal insufficiency > 2) G4: Life-threatening consequences (eg, CNS hemorrhage or thrombosis/embolism or renal failure)	Hold ICPI and discuss resumption with patient only after taking into account the risks and benefits, noting that there are currently no data to recommend restarting ICPI therapy Hematology consult In conjunction with hematology, initiate PEX according to existing guidelines with further PEX dependent on clinical progress Administer methylprednisolone 1 g IV daily for 3 days, with the first dose typically administered immediately after the first PEX May offer rituximab
8.3 Hemolytic uremic syndrome	
Definition: A disorder characterized by a form of thrombotic microangiopathy with renal failure, hemolytic anemia, and severe thrombocytopenia. Signs and symptoms of hemolytic uremic syndrome can include: Bloody diarrhea Decreased urination or blood in the urine	

8.0 Hematologic Toxicities	

Abdominal pain, vomiting, and occasionally fever            Pallor            Small, unexplained bruises or bleeding from the nose and mouth Fatigue and irritability            Confusion or seizures            High blood pressure            Swelling of the face, hands, feet, or entire body
	

Diagnostic work-up            History and physical examination (special consideration for new history of high-risk drugs, hypertension, or cardiac causes) CBC with indices            Blood smear morphology. Note that the presence of schistocytes on smear is critical for diagnosis.            Serum creatinine            ADAMTS13 (to rule out TTP)            Homocysteine/methylmalonic acid            Complement testing C3, C4, CH50 (complement inhibitory antibodies for suspected familial)            Evaluate reticulocyte count and mean corpuscular volume            Evaluation of infectious cause, including screening for EBV, CMV, HHV6            Evaluation for nutritional causes of macrocytosis (B12 and folate)            Pancreatic enzymes            Evaluation for diarrheal causes, shiga toxin, Escherichia coli 0157, etc            Direct antibody test (Coombs test), haptoglobin, LDH, and other etiologies of anemia            Evaluation for common drugs causing hemolysis (tacrolimus, cyclosporine, sirolimus, etc)            Evaluation for concurrent confusion
	
Grading	Management

G1-2: Evidence of RBC destruction (schistocytosis) without clinical consequences of anemia, thrombocytopenia Grade 2            G3: Laboratory findings with clinical consequences (eg, renal insufficiency, petechiae)            G4: Life-threatening consequences (eg, CNS thrombosis/ embolism or renal failure)
	
Continue ICPI with close clinical follow-up and laboratory evaluation            Supportive care Permanently discontinue ICPI            Begin therapy with eculizumab therapy 900 mg weekly for four doses, 1,200 mg week 5, then 1,200 mg every 2 weeks            Red blood transfusion according to existing guidelines

8.4 Aplastic anemia	
Definition: Condition in which the body stops producing enough new blood cells	

Diagnostic work-up            History and physical examination (close attention to medications, exposure to radiation, toxins, recent viral infections) CBC, smear, reticulocyte count            Viral studies, including CMV, HHV6, EBV, parvovirus            Nutritional assessments including B12, folate, iron, copper, ceruloplasmin, vitamin D            Serum LDH, renal function            Work-up for infectious causes            Identify marrow hypo/aplasia            Bone marrow biopsy and aspirate analysis            Peripheral blood analysis, including neutrophil count, proportion of GPI-negative cells by flow for PNH            Flow cytometry to evaluate loss of GPI-anchored proteins            Type and screen patient for transfusions and notify blood bank that all transfusions need to be irradiated and filtered
	
Grading	Management

G1: Nonsevere, < 0.5 polymorphonuclear cells x 10^9/L hypocellular marrow, with marrow cellularity < 25%, peripheral platelet count . 20,000, reticulocyte count < 20,000
	
Hold ICPI and provide growth factor support and close clinical follow-up, and laboratory evaluation            Supportive transfusions as per local guidelines

8.0 Hematologic Toxicities	
G2: Severe, hypocellular marrow < 25% and two of the following: ANC < 500, peripheral platelet < 20,000, and reticulocyte < 20,000	Hold ICPI and provide growth factor support and close clinical laboratory evaluations daily Administer ATG + cyclosporine; HLA typing and evaluation for bone marrow transplantation if patient is candidate; all blood products should be irradiated and filtered Supportive care with granulocyte colony-stimulating factor may be added in addition
G3-4: Very severe, ANC > 200, platelet count > 20,000, reticulocyte count > 20,000, plus hypocellular marrow > 25%	Hold ICPI and monitor weekly for improvement; if not resolved, discontinue treatment until AE has reverted to G1 Hematology consult, growth factor support Horse ATG plus cyclosporine If no response, repeat immunosuppression with rabbit ATG plus cyclosporine, cyclophosphamide For refractory patients, consider eltrombopag plus supportive care
8.5 Lymphopenia	
Definition: An abnormally low level of lymphocytes in PB; for adults, counts of < 1,500/mm 	

Diagnostic work-up
 
History and physical examination (special attention for lymphocyte-depleting therapy such as fludarabine, ATG, corticosteroids, cytotoxic chemotherapy, radiation exposure, etc, as well as history of autoimmune disease, family history of autoimmune disease) Evaluation of nutritional state as cause
 
Spleen size
 
CBC with differential, peripheral smear and reticulocyte counts
 
CXR for evaluation of presence of thymoma
 
Bacterial cultures and evaluation for infection (fungal, viral, bacterial specifically CMV/HIV)
	
Grading	Management
G1-2: 500-1,000 PB lymphocyte count G3: 250-499 PB lymphocyte count G4: < 250 PB lymphocyte count	Continue ICPI Continue ICPI, checking CBC weekly for monitoring, initiation of CMV screening Consider holding ICPI Initiate Mycobacterium avium complex prophylaxis and Pneumocystis jirovecii prophylaxis, CMV screening, HIV/hepatitis screening if not already done May consider EBV testing if evidence of lymphadenopathy/hepatitis, fevers, hemolysis consistent with lymphoproliferative disease
8.6 Immune thrombocytopenia	
Definition: An autoimmune disorder characterized by immunologic destruction of otherwise normal platelets	

Diagnostic work-up
 
History and physical examination (special attention for lymphocyte-depleting therapy, such as fludarabine, ATG, corticosteroids, cytotoxic therapy) Family history of autoimmunity or personal history of autoimmune disease
 
History of viral illness
 
CBC
 
Peripheral blood smear, reticulocyte count
 
Bone marrow evaluation only if abnormalities in the above test results and further investigation is necessary for a diagnosis
 
Patients with newly diagnosed immune thrombocytopenia should undergo testing for HIV, hepatitis C virus, hepatitis B virus, and Helicobacter pylori Direct antigen test should be checked to rule out concurrent Evan syndrome
 
Nutritional evaluation
	

8.0 Hematologic Toxicities	
Bone marrow evaluation if other cell lines affected and concern for aplastic anemia	
Grading	Management
G1: Platelet count < 100/ $\mu$ L G2: Platelet count < 75/ $\mu$ L	Continue ICPI with close clinical follow-up and laboratory evaluation Hold ICPI but monitor for improvement; if not resolved, interrupt treatment until AE has reverted to G1 Administer prednisone 1 mg/kg/d (dosage range, 0.5-2 mg/kg/d) orally for 2-4 weeks after which time this medication should be tapered over 4-6 weeks to the lowest effective dose IVIG may be used in conjunction with corticosteroids if a more-rapid increase in platelet count is required.
G3: Platelet count < 50/ $\mu$ L	Hold ICPI but monitor for improvement; if not resolved, interrupt treatment until AE has reverted to G1
G4: Platelet count < 25/ $\mu$ L	Hematology consult Prednisone 1-2 mg/kg/d (oral or IV depending on symptoms) If worsening or no improvement, 1-2 mg/kg/d prednisone equivalents and permanently discontinue treatment IVIG used with corticosteroids when a more-rapid increase in platelet count is required If IVIG is used, the dose should initially be 1 g/kg as a one-time dose. This dosage may be repeated if necessary If previous treatment with corticosteroids and/or IVIG unsuccessful, subsequent treatment may include rituximab, thrombopoietin receptor agonists, or more-potent immunosuppression (From American Society of Hematology guideline on immune thrombocytopenia  ; consult for further details)
8.7 Acquired hemophilia	
Definition: Disorder caused by the development of autoantibodies (inhibitors) directed against plasma coagulation factors	
Diagnostic work-up Full blood count to assess platelet number, fibrinogen, PT, PTT, INR; the typical finding in patients with acquired hemophilia A is a prolonged activated PTT with a normal PT MRI, CT, and ultrasonography may be indicated to localize, quantify, and serially monitor the location and response of bleeding Medication review to assess for alternative causes Determination of Bethesda unit level of inhibitor	
Grading	Management
G1: Mild, 5%-40% of normal factor activity in blood, 0.05-0.4 IU/mL of whole blood	Hold ICPI and discuss resumption with patient only after taking into account the risks and benefits Administer 0.5-1 mg/kg/d prednisone Transfusion support as required Treatment of bleeding disorders with hematology consult
G2: Moderate, 1%-5% of normal factor activity in blood, 0.01- 0.05 IU/mL of whole blood	Hematology consult Administration of factor replacement (choice based on Bethesda unit of titer) Administer 1 mg/kg/d prednisone 6 rituximab (dose, 375 mg/m  weekly for 4 weeks) and/or cyclophosphamide

8.0 Hematologic Toxicities	
	
(dose, 1-2 mg/kg/d); choice of rituximab v cyclophosphamide is patient specific and should be done with assistance of hematology consult; prednisone, rituximab, and cyclophosphamide should be given for at least 5 weeks
 
Factors should be provided to increase level during bleeding episodes, with choice of factor based on presence or absence of inhibitor

G3-4: Severe, < 1% of normal factor activity in blood, < 0.01 IU/mL of whole blood	
Permanently discontinue ICPI
 
Admit patient
 
Hematology consult
 
Administration of factor replacement, choice based on Bethesda unit level of inhibitor Bypassing agents may be used (factor VII, factor VIII inhibitor bypass activity); caution should be taken in the elderly and those with coronary artery disease
 
Prednisone 1-2 mg/kg/d (oral or IV depending on symptoms) 6 rituximab (dose, 375 mg/m^2 weekly for 4 weeks) and/or cyclophosphamide (dose, 1-2 mg/kg/d).
 
Transfusion support as required for bleeding
 
If worsening or no improvement add cyclosporine or immunosuppression/immunoadsorption


Additional considerations: The American Heart Association requires specialist clinical and laboratory expertise. Consult and/or transfer to a specialist center is often appropriate. If consultation with or transfer to a hemophilia center is not immediately possible, then investigation and treatment should be initiated while a liaison is being established.
 
All recommendations are expert consensus based, with benefits outweighing harms, and strength of recommendations are moderate.
 
Abbreviations: AE, adverse event; ANC, absolute neutrophil count; ATG, antithymocyte globulin; CBC, complete blood count; CMV, cytomegalovirus; CNS, central nervous system; CT, computed tomography; CXR, chest x-ray; DIC, disseminated intravascular coagulation; EBV, Epstein-Barr virus; ECG, electrocardiogram; ER, extended release; FE, ferritin; G, Grade; GPI, glycosylphosphatidylinositol; Hgb, hemoglobin; HHV6, human herpesvirus 6; HIV, human immunodeficiency virus; HLA, human leukocyte antigen; ICPI, immune checkpoint inhibitor; INR, international normalized ratio; irAE, immune-related adverse event; IV, intravenous; IVIG, intravenous immunoglobulin; LDH, lactate dehydrogenase; LLN, lower limit of normal; MRI, magnetic resonance imaging; NSAID, nonsteroidal anti-inflammatory drug; PB, peripheral blood; PEX, plasma ex-change; PNH, paroxysmal nocturnal hemoglobinuria; PT, prothrombin time; PTT, partial thromboplastin time; RBC, red blood cell count; TTP, thrombotic thrombocytopenic purpura.
	

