2.1.1.9 Eastern Cooperative Oncology Group (ECOG) performance status  $\leq 2$  (see Section 16.2)

2.1.1.10 Required laboratory values reflective of organ function are listed below:

- Absolute neutrophil count  $\geq 1500/\mu\text{L}$
- Platelets  $\geq 100,000/\mu\text{L}$
- Hemoglobin  $\geq 9$  g/dL (erythrocyte transfusions are allowed to achieve acceptable Hgb)
- AST(SGOT)/ALT(SGPT)  $\leq 1.5 \times$  institutional upper limit of normal (ULN) with the following exception:
  - Patients with liver involvement who have AST and ALT  $\leq 5 \times$  ULN may be enrolled.
- Total bilirubin within normal limits with the following exceptions:
  - Patients with known Gilbert disease who have serum bilirubin level  $\leq 3$  ULN may be enrolled.
  - Patients with tumor liver involvement bilirubin with  $\leq 3.0 \times$  ULN.
- INR and aPTT  $\leq 1.5 \times$  ULN
  - This applies only to patients who are not receiving therapeutic anticoagulation; patients receiving therapeutic anticoagulation (such as low-molecular-weight heparin or warfarin) should be on a stable dose.
- Creatinine clearance (CrCl)  $\geq 30$  mL/min/1.73 m^2 (GFR may be used in place of CrCl. Creatinine clearance or eGFR should be calculated per institutional standard)

2.1.1.11 The effects of M7824 on the developing human fetus are unknown. For this reason, women of child-bearing potential and men must agree to use strict and effective contraception (hormonal or barrier method of birth control; abstinence) during treatment

and for at least 65 days for women and 125 days for men, after the last dose of M7824 administration. Should a woman become pregnant or suspect she is pregnant while she or her partner is participating in this study, she should inform her treating physician immediately.

- 2.1.1.12 Human immunodeficiency virus (HIV) positive patients are eligible if on stable dose of highly active antiretroviral therapy (HAART), CD4 counts are greater than 350 cells/mm^3 and viral load is undetectable.
- 2.1.1.13 Patients with previously treated brain or central nervous system (CNS) metastases are eligible provided that the subjects have recovered from any acute effects of radiotherapy and is not requiring steroids, and any whole brain radiation therapy or any stereotactic radiosurgery was completed at least 2 weeks prior to M7824 administration.

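### Table A8, section 8.6, prints the immune thrombocytopenia grade limits 1000 times too low: <100, <75, <50 and <25 platelets per microlitre

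*Combined protocol and SAP*

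**What the plan says.** Section 8.6 of Table A8 sets four platelet limits, each labelled per microlitre: "G1: Platelet count < 100" for the mildest grade, below 75 for Grade 2, "G3: Platelet count < 50" and "G4: Platelet count < 25".

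Actions depend on these grades:
- Grade 1: drug continues with monitoring.
- Grade 2: "Hold ICPI but monitor for improvement; if not resolved, interrupt treatment until AE has reverted to G1", with a steroid course: "Administer prednisone 1 mg/kg/d (dosage range, 0.5-2 mg/kg/d) orally for 2-4 weeks".
- Grades 3 and 4: the hold rule again, a hematology consult, prednisone at 1-2 mg/kg/d, and permanent discontinuation if the count worsens or fails to improve.

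Neither section 8.6 nor the abbreviation list at the end of Table A8 says that the counts are in thousands.

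Elsewhere, 2.1.1.10 requires at least 100,000 platelets per microlitre at entry. Section 8.4 of the same table (aplastic anemia, Grade 2) uses "two of the following: ANC < 500, peripheral platelet < 20,000, and reticulocyte < 20,000". Section 8.5 (lymphopenia) defines the condition with "for adults, counts of < 1,500/mm" (per cubic millimetre) and grades it at 500-1,000, 250-499 and below 250.

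**The concern.** A limit of 100 platelets per microlitre is far outside the range in which the rest of the protocol works. A reader coming from section 8.5 has just seen whole cell counts and has no cue to switch to thousands in 8.6.

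The limits are decision thresholds for holding drug, giving steroids and resuming treatment. Taken at face value, the hold is never triggered at any realistic count, and the resumption condition never restrains anyone, because almost every patient already lies above the Grade 1 limit. Bleeding is an adverse event of special interest (8.1.6) and an identified risk of the drug (Table 6), so the platelet action limits ought to be right.

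**Working it through.** **Inputs**

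- Printed limits (Table A8, 8.6): 100, 75, 50 and 25 per microlitre.
- Eligibility floor (2.1.1.10): 100,000 per microlitre.
- Aplastic anemia platelet limit (Table A8, 8.4): 20,000, no unit printed.
- Lymphopenia definition (Table A8, 8.5): below 1,500 per mm³.

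**Scale factor.** Eligibility and section 8.6 share analyte and unit, so they compare directly: 100,000 / 100 = 1000.

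**Order-of-magnitude check.** The section 8.4 value is 20,000 / 100 = 200 times the printed Grade 1 limit and 20,000 / 25 = 800 times the printed Grade 4 limit. It carries no unit, so it supports the order of magnitude and not the exact factor.

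**Unit convention next door.** 1 mm³ = 1 microlitre, so the section 8.5 definition is below 1,500 per microlitre, a full count.

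**Rescaled limits**

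| Grade | Printed (per µL) | × 1000 (per µL) | Equivalent (× 10⁹/L) |
|---|---|---|---|
| 1 | <100 | <100,000 | <100 |
| 2 | <75 | <75,000 | <75 |
| 3 | <50 | <50,000 | <50 |
| 4 | <25 | <25,000 | <25 |

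The last column uses 10⁶ microlitres per litre; for example, 75,000 × 10⁶ = 75 × 10⁹ per litre. The rescaled Grade 1 limit equals the eligibility floor.

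**Grade assigned to sample counts**

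| Count (per µL) | As printed | After × 1000 |
|---|---|---|
| 99,000 | none | 1 |
| 74,000 | none | 2 |
| 49,000 | none | 3 |
| 24,000 | none | 4 |
| 10,000 | none | 4 |
| 5,000 | none | 4 |

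A count of 10,000 is 10,000 / 100 = 100 times the printed Grade 1 limit, so it is ungraded; it is below 25,000, so it is Grade 4 after rescaling.

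**Could it be a PDF-reading fault?** Unlikely. The per-microlitre unit reads cleanly in all four rows and the numbers are consistent with one another. A multiplier would have had to vanish four times, while a × 10⁹/L multiplier survived in section 8.4 of the same table.

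**The case against.** The strongest reply is that little turns on section 8.6:

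- Severity is graded by CTCAE v5.0 (3.3.1.8, 6.4, 8.1.4).
- Section 3.3.1.2 stops treatment permanently for any Grade 4 drug reaction, with limited exceptions, and Table 2 lists Grade 4 immune thrombocytopenia for permanent discontinuation.
- Section 3.3.1.8 gives general suspend, steroid and stop rules by CTCAE grade.
- The body never cites Appendix C by name, the table of contents does not list it, and Table 2 sends investigators to the NCCN guideline.

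All of this stands, and it limits the harm. A severe drug-related platelet fall would be handled without section 8.6, and what that section adds is mostly steroid and immunoglobulin detail. It does not make the printed limits right. Section 3.3.1.8 gives ASCO organ-specific management precedence over its general rules. Table A8 is guidance of that kind, although treating it as the text meant is an inference.

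A second objection is that the anchors are uneven. Section 8.4 has no platelet unit and shows other damage in its grade rows, the lymphocyte grades also lack a unit, and an entry criterion is not a grade limit. This also stands. The exact factor rests mainly on 2.1.1.10, and the other anchors only support the scale.

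**Conclusion.** The concern holds. All four limits in section 8.6 are wrong as written, by one common factor of 1000, and at any realistic count the section's own rules never take effect.

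The severity is minor. CTCAE grading and the Grade 4 stopping rules in the body provide a safeguard, and clinicians would probably read the values as thousands. Objective response rate, the Simon two-stage designs, sample size and data collection are not affected.

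The factor is inferred from the protocol's other platelet figures, chiefly the eligibility floor. Neither CTCAE nor the source of Table A8 is among the documents, so the corrected boundaries cannot be confirmed here. Nothing is claimed about whether the slip arose in the protocol or in text it reproduced.

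**What to change.** Restate the section 8.6 limits as <100,000, <75,000, <50,000 and <25,000 per microlitre, or equivalently <100, <75, <50 and <25 × 10⁹/L. The sponsor should first confirm them against CTCAE v5.0, which 6.4 adopts, and can usefully check the guideline from which Table A8 was taken as well.

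The cost is four corrected limits in Appendix C at the next amendment, with no change to data collection, sample size or analysis.
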